12.2 Secondary Analysis

We will determine secondary responses for: 1) tumor necrosis; 2) proliferation index; and 3) ERK/MEK phosphorylation. These assays will be exploratory and not subjected to a prospective statistical plan for analysis. Tumor necrosis % will be estimated according the standard surgical pathology techniques. Proliferation index will be measured by percentage of cells in mitosis and Ki 67 staining per standard surgical pathology assays. The ratio of unphosphorylated to phosphorylated ERK and MEK will be done using standard phosphorylation specific antibodies on tumor tissue specimens in [name] lab according to his lab's SOPs. See Section 10 for details.

12.3 Sample Size

11 to 21 patients (9 to 17 evaluable patients). See Section 12.1

12.4 Accrual estimates

We estimate 3 to 6 patients will be accrued among collaborating institutions annually. This is a very rare disease, incidence 0.5/ million estimated. Stanford sees and evaluates outside pathology on about 5 cases per year and our collaborating centers estimate about the same.

12.5 Feasibility and safety assessment

Because this is a very rare disease, our assumptions concerning the ability to accrue in a timely way are considerably uncertain. Therefore, at each annual review, should the accrual in the preceding year be less than 3 patients, we will re-evaluate the feasibility of conducting this protocol and either modify the protocol or close the protocol. Also as part of that annual review, if the cumulative rate of completion of 6 weeks of dabrafenib and trametinib treatment as specified in Section 4 is not achieved in at least 2/3 of all subjects, we will review the feasibility of administering treatment on this study and modify or close the protocol.

Safety data, collected as specified in the study calendar in section nine, will be summarized in tabular form using the CTCAE v4.03 for AE description and grading. Cumulative safety data and all SAE reports will be reviewed by investigators both annually and at the end of the first stage of accrual. Should less than 2/3 of patients enrolled at any of these annual reviews or first stage analysis not complete the protocol treatment as stipulated in this protocol, the protocol will either be amended to address these safety issues or the protocol will be closed to further accrual. High-grade AEs alone are not to be construed as an indication to stop accrual or amend the protocol as long as treatment of those AEs per standards of care and modifications per Section 6 allow for completion of treatment as specified in Section 4. Reporting of SAEs is covered in Section 7.2.

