11 REGULATORY CONSIDERATIONS

11.1 Institutional Review of Protocol

The protocol, the proposed informed consent and all forms of participant information related to the study (e.g. advertisements used to recruit participants) will be reviewed and approved by the Stanford IRB and Stanford Cancer Institute Scientific Review Committee (SRC). Any changes made to the protocol will be submitted as a modification and will be approved by the IRB prior to implementation. The Protocol Director will disseminate the protocol amendment information to all participating investigators. All participating sites will similarly have the informed consent document and protocol reviewed and approved by their local IRB and scientific review committee. There is to be only one version of the protocol to be used across all participating sites and no site can individually modify or amend the protocol at their site alone. That is, all protocol amendments and modifications must be reviewed and approved by all institutions' relevant review boards.

11.2 Data and Safety Monitoring Plan:

The Stanford Cancer Institute Data and Safety Monitoring Committee (DSMC) will be the monitoring entity for this study. The DSMC will audit study-related activities to determine whether the study has been conducted in accordance with the protocol, local standard operating procedures, FDA regulations, and Good Clinical Practice (GCP). This may

include review of the following types of documents participating in the study: regulatory binders, case report forms, eligibility checklists, and source documents. In addition, the DSMC will regularly review serious adverse events and protocol deviations associated with the research to ensure the protection of human subjects. Results of the DSMC audit will be communicated to the IRBs of all participating institutions and the appropriate regulatory authorities at the time of continuing review, or in an expedited fashion, as needed.

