12 STATISTICAL CONSIDERATIONS

12.1 Statistical Design and primary analysis

We propose a two stage Optimal design per Simon, *et al.* (Simon R, 1989. *Controlled Clinical Trials*. 10:1-10), and using the UNC calculator:

<http://www.csc.unc.edu/csc/aivanova/SimonsTwoStageDesign.aspx>

The null hypothesis that the true response rate is 0.05 will be tested against a one-sided alternative. In the first stage, 9 evaluable patients will be accrued. If there is less than one response (defined in Section 10.1) in these 9 patients, the study will be stopped. If at the time of the 9th patient's enrollment there has not been at least one centrally documented response, accrual will stop until responses have been centrally determined for the first nine patients. Otherwise, 8 additional evaluable patients will be accrued for a total of

17 evaluable patients. The null hypothesis will be rejected if 3 or more responses are observed in 17 patients. We will allow for up to 11 patients in the first stage and up to 10 patients in the second stage to account for patient drop-out / unevaluable patients. This design yields a type I error rate of 0.0466 and power of 0.8122 when the true response rate is 0.25. We believe that anything below a response rate of 25% would not be clinically meaningful given the potential risks of dabrafenib and trametinib. The likelihood of stopping early if the null hypothesis is true will be 0.63. A response rate of 25% or higher, in the context of other promising secondary endpoint results such as a high % of tumor necrosis, would warrant further study.

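### The safety completion rule in Section 12.5 is inverted: as worded it requires amendment or closure when completion exceeds 1/3, including 100%, and is silent when 2/3 or more fail to complete

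*Combined protocol and SAP*

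**What the plan says.** Section 12.5 contains two rules based on treatment completion.

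- **Feasibility rule.** It opens "Also as part of that annual review, if the cumulative rate of completion of 6 weeks" and applies when completion of treatment "as specified in Section 4 is not achieved in at least 2/3 of all subjects". The consequence is to review feasibility and modify or close the protocol. It is tied to the annual review only.
- **Safety rule.** Cumulative safety data and SAE reports are "reviewed by investigators both annually and at the end of the first stage of accrual". The trigger is: "Should less than 2/3 of patients enrolled at any of these annual reviews or first stage analysis not complete the protocol treatment". The consequence is mandatory: "the protocol will either be amended to address these safety issues or the protocol will be closed to further accrual".

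The sentence after the safety rule says that high-grade adverse events alone are no reason to stop or amend, provided that their treatment and "modifications per Section 6 allow for completion of treatment as specified in Section 4". Completion is therefore treated as the reassuring outcome.

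**The concern.** The safety sentence counts patients who do *not* complete and acts when their share is *below* 2/3. That is the reverse of the feasibility sentence, and of the sentence that follows, where completion is the reason to carry on. No other part of the protocol restates the rule in the right direction.

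Three things are at stake:

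- **High completion.** Read literally, investigators must amend or close a well-tolerated trial at every annual review and at the first-stage review. If they ignore the sentence, they depart from a written rule, and Section 11.2 has the DSMC audit conduct against the protocol.
- **Low completion at the end of stage 1.** The feasibility rule does not apply at this review, so the inverted sentence is the only completion rule there. It says nothing when completion is 1/3 or less.
- **No other threshold.** This is the only numerical trigger in the safety paragraph, and the monitoring plan in Section 11.2 gives none.

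**Working it through.** **Inputs**

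- Safety trigger (Section 12.5): share of enrolled patients not completing is below 2/3.
- Feasibility trigger (Section 12.5): cumulative share completing is below 2/3, at annual review.
- First-stage size (Section 12.1): 9 evaluable patients; "We will allow for up to 11 patients in the first stage".
- Accrual (Section 12.4): 3 to 6 patients per year.
- Completion rate: none is given. The rates in step 4 are assumptions.

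The plan states no operating characteristics for this rule, so there is no figure to reproduce.

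**Step 1: the trigger as written.** Let c of n enrolled patients complete. The sentence fires when (n − c)/n < 2/3, which is the same as c/n > 1/3. With c = n the left side is 0, which is below 2/3, so full completion fires it. With c = 0 the left side is 1, so it does not fire when nobody completes.

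**Step 2: comparison with the feasibility direction.** That trigger is c/n < 2/3. If both sentences count the same completions, then at an annual review:

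- c/n of 2/3 or more: only the safety sentence fires;
- c/n above 1/3 and below 2/3: both fire;
- c/n of 1/3 or less: only the feasibility sentence fires.

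**Step 3: numbers of completers that trigger each rule.**

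| Enrolled | Safety sentence as written | Feasibility direction |
|---|---|---|
| 9 | 4–9 | 0–5 |
| 10 | 4–10 | 0–6 |
| 11 | 4–11 | 0–7 |

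At the first-stage review only the safety sentence is in force. With 9, 10 or 11 enrolled, 0 to 3 completers trigger nothing there. The right-hand column shows what a rule in the feasibility direction would do if it applied at that review.

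**Step 4: probability of firing.** For an assumed true completion rate p:

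- as written: the sum over c = 4 to n of C(n,c) p^c (1 − p)^(n − c);
- feasibility direction: the same terms summed over c = 0 to 5 for n = 9, and c = 0 to 7 for n = 11.

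| Assumed p | n = 9, as written | n = 9, feasibility direction | n = 11, as written | n = 11, feasibility direction |
|---|---|---|---|---|
| 0.9 | >0.999 | 0.008 | >0.999 | 0.019 |
| 0.8 | 0.997 | 0.086 | >0.999 | 0.161 |
| 0.5 | 0.746 | 0.746 | 0.887 | 0.887 |
| 0.3 | 0.270 | 0.975 | 0.430 | 0.996 |

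As written, the chance of action rises with completion; a completion safeguard should do the opposite.

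**Step 5: length of the first-stage gap.** Enrolling 9 to 11 patients at 3 to 6 per year takes from 9/6 = 1.5 years to 11/3 ≈ 3.7 years, so stage 1 need not end at an annual review. The next annual review could be up to 12 months later, which is up to 3 to 6 further patients at the stated rate.

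**The case against.** The strongest reply is that nobody would apply the sentence literally. The amendment it calls for is meant to address safety issues, and at full completion this rule identifies none. The preceding paragraph uses the same 2/3 threshold in the right direction, and the following sentence treats completion as reassuring. Intent is recoverable, so closure of a well-completed trial is unlikely. That stands as a limit on the expected harm, but it does not make the sentence correct.

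Low completion is also mostly covered. The feasibility rule acts at each annual review, and at the stated accrual at least one annual review precedes the end of stage 1. Investigators review cumulative safety data at that point, and under Section 11.2 "the DSMC will regularly review serious adverse events and protocol deviations associated with the research". This also stands. What remains uncovered is a completion rule at the first-stage review itself.

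Finally, the two sentences may not count the same thing. One refers to 6 weeks of treatment and the other to the protocol treatment as stipulated; under Section 4, patients whose disease is not amenable to resection continue indefinitely. The three zones in step 2 therefore depend on a shared definition. The inversion does not: whatever counts as completion, the safety sentence fires when more than 1/3 achieve it.

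**Conclusion.** The concern holds. As worded, the safety sentence requires amendment or closure whenever completion exceeds 1/3, including 100%, and requires nothing when 2/3 or more do not complete. At the first-stage review it fires at 4 or more completers among 9 to 11 enrolled and is silent at 0 to 3. These ranges follow from the text without assumptions. The probabilities rest on assumed completion rates and describe the literal reading, not a forecast of what investigators would do.

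The type I error and power in Section 12.1 are unaffected. The practical harm is limited by recoverable intent and by the annual feasibility rule. It should nevertheless be corrected, because it is a mandatory trial-level decision rule that says the opposite of what its own section needs.

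**What to change.** Reconcile the two sentences in Section 12.5 by deleting the 'not' before 'complete' in the safety sentence. It then acts when fewer than 2/3 of enrolled patients complete the protocol treatment, at both the annual and the first-stage reviews. The trigger becomes 0–5 completers of 9, 0–6 of 10 and 0–7 of 11. In the same edit, it would help to state whether both sentences count completion of the same 6 weeks of treatment.

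The correction is one word. It adds no patients, visits or procedures and leaves the Simon design unchanged. It needs the amendment approval described in Section 11.1 and is best made before the next review applies the rule.

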If a subject misses a dose of dabrafenib, the subject may take the dose immediately if the next dose is scheduled for at least 6 hours later. If the next scheduled dose of dabrafenib is due in less than 6 hours, the subject should skip the dose and resume dabrafenib dosing at the next scheduled dose. If a subject misses a dose of trametinib, the subject may take the dose immediately if the next dose is scheduled for at least 12 hours later.

Patients whose tumors are amenable to surgical resection will continue dosing continuously for at least 6 weeks and proceed to surgery between weeks 6 and 7, without dose interruption. Patients undergoing surgical resection will continue dabrafenib and trametinib until it is necessary to take nothing by mouth in the hours preceding surgery, but **ideally the patients will be dosed with dabrafenib and trametinib within 12 hours of the surgical resection**. Patients whose tumors are grossly completely resected will not resume dabrafenib and trametinib. Patients whose tumors are not resected completely have the option to resume the dabrafenib and trametinib at the dose they were receiving immediately prior to surgery if ALL of the following criteria are met:

1. Prior to surgery the patient did not have AEs or progression which necessitated dabrafenib or trametinib cessation.
2. The patient has recovered from surgery without unexpected complication.
3. At least 1 week has passed since surgery.
4. The patient has evaluable residual tumor.
5. No more than 6 weeks has elapsed since surgery.

Patients whose disease is judged to be not amenable to resection will continue dabrafenib and trametinib indefinitely as long as there has not been tumor progression either by RECIST v1.1 or clinical progression criteria, there have not been unacceptable adverse events and the patient has not decided to discontinue for other reasons.

Clinical evaluations for protocol purposes will take place according to the schedule defined in Section 9. Dose modifications will be according to the guidelines in Section 6.

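### The two-thirds safety rule in Section 12.5 is worded the wrong way round, and the completion it counts has no stated endpoint for patients who are not resected

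*Combined protocol and SAP*

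**What the plan says.** Section 12.5 contains two rules with a 2/3 threshold.

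- **Feasibility rule, at each annual review.** The event has a duration. The team reviews feasibility, then modifies or closes the protocol, when this standard is missed: "cumulative rate of completion of 6 weeks of dabrafenib and trametinib treatment as specified in Section 4 is not achieved in at least 2/3".
- **Safety rule, at each annual review and at the end of stage 1.** The event has no duration: "Should less than 2/3 of patients enrolled at any of these annual reviews or first stage analysis not complete the protocol treatment". The consequence is mandatory, because the same sentence states: "not complete the protocol treatment as stipulated in this protocol, the protocol will either be amended to address these safety issues". Ending accrual is the only alternative it offers. The next sentence exempts high-grade adverse events from being a reason to stop on their own, as long as their treatment and "modifications per Section 6 allow for completion of treatment as specified in Section 4". That sentence gives no duration either.

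Section 4.0 sets out two treatment courses. Patients with resectable tumours "will continue dosing continuously for at least 6 weeks and proceed to surgery between weeks 6 and 7". For the others, "Patients whose disease is judged to be not amenable to resection will continue dabrafenib and trametinib indefinitely", provided there is no progression, no unacceptable adverse event and no decision by the patient to stop. The study calendar in Section 9 likewise continues both drugs in unresected patients until the disease progresses or treatment is not tolerated. Section 4.2 lists adverse events, progression and withdrawal of consent as reasons to stop. It has no category for having completed treatment.

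**The concern.** A rule that obliges the team to amend or close should give one answer for one set of patients. This one does not, for two separate reasons.

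**Direction.** The printed trigger is a low proportion of patients who do *not* complete. Few non-completers is the good outcome, so the wording reverses the evident purpose.

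**Event.** Treatment of a resectable patient has a natural end at surgery. An unresected patient is, at any review, either still on drug or has stopped for progression, toxicity or choice. The documents do not say which of these counts as completing the protocol treatment. If none does, the rule responds to the case mix rather than to tolerability, and a patient who is still benefiting on drug counts against safety.

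At stake is an unnecessary amendment, or at worst a closure, in a rare-disease trial that expects 3 to 6 patients a year (Section 12.4).

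**Working it through.** **Inputs.** Stage 1 has 9 evaluable patients and up to 11 enrolled (Section 12.1). Accrual is 3 to 6 a year (Section 12.4). The threshold is 2/3 (Section 12.5). The share of patients not resected, q, is not in the documents, so it is an assumption and is varied from 0.1 to 0.6.

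**The plan's own figures.** Section 12.5 gives no operating characteristics for the 2/3 rule, so there is none to reproduce. The design figures in Section 12.1 do reproduce. Early stopping under the null is 0.95^9 = 0.6302 (stated 0.63). Rejection probability is the sum over x = 1 to 9 of P(X1 = x) × P(X2 ≥ 3 − x), with X1 ~ Bin(9, p) and X2 ~ Bin(8, p). This gives 0.0466 at p = 0.05 and 0.8122 at p = 0.25, as stated.

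**Step 1: the literal trigger.** It fires if non-completers / n < 2/3.

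- n = 9: 2/3 × 9 = 6, so it fires at 0 to 5 non-completers.
- n = 11: 2/3 × 11 = 7.33, so it fires at 0 to 7 non-completers.

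It therefore fires with certainty when everyone completes. Scoring unresected patients as non-completers makes firing *less* likely under this wording: at n = 9 the probability falls from 1.000 at q = 0 to 0.517 at q = 0.6.

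**Step 2: evident direction, unresected patients scored as non-completers, no toxicity.** It fires if (n − U) / n < 2/3, where U is the number unresected.

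- n = 9: U = 3 gives 6/9 = 67% and does not fire; U = 4 gives 5/9 = 56% and fires.
- n = 11: U = 3 gives 8/11 = 73% and does not fire; U = 4 gives 7/11 = 64% and fires.

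The probability of firing at a single review is P(Bin(n, q) ≥ smallest firing U). For n = 9 and q = 0.3 this is 1 − (0.040 + 0.156 + 0.267 + 0.267) = 0.270.

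| Patients | Fires at U ≥ | q = 0.1 | 0.2 | 0.3 | 0.4 | 0.5 | 0.6 |
|---|---|---|---|---|---|---|---|
| 3 | 2 | 0.028 | 0.104 | 0.216 | 0.352 | 0.500 | 0.648 |
| 6 | 3 | 0.016 | 0.099 | 0.256 | 0.456 | 0.656 | 0.821 |
| 9 | 4 | 0.008 | 0.086 | 0.270 | 0.517 | 0.746 | 0.901 |
| 11 | 4 | 0.019 | 0.161 | 0.430 | 0.704 | 0.887 | 0.971 |

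**Step 3: evident direction, completion means 6 weeks for everyone.** With perfect tolerability and all patients past week 6, the score is 9/9 or 11/11 and the probability of firing is 0. It takes 4 or more true non-completers of 9 or of 11 to fire.

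**Step 4: is adding the 6-week milestone enough?** No, for two reasons.

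- If the direction is left as printed, 0/9 non-completers is still below 2/3 and the rule still fires.
- Patients who have not yet reached week 6 also need a rule. If 3 patients are enrolled in a year and 2 joined less than 6 weeks before the review, only 1/3 can have completed. The corrected direction then fires with no toxicity.

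**The case against.** A reader might infer that unresected patients can never complete protocol treatment, so that the rule is bound to force closure even with perfect tolerability. The documents do not support that reading, for four reasons.

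- **The 6-week meaning is available one paragraph earlier.** The feasibility rule uses it with the same threshold and the same reference to Section 4, and unresected patients can meet it. Every trigger in Step 2 then disappears.
- **A second benign reading exists.** A patient who is still on drug, or who was treated until progression, can be said to have been treated as stipulated. No text says otherwise. The rule's stated purpose of addressing safety issues also argues against counting a patient who tolerates treatment as a failure.
- **The unresected share may be low.** Section 2.3 describes a population mostly with mandibular bone involvement and without metastases, and a design meant not to delay surgery unduly. Nothing in the documents supports a share of 40% or more.
- **Closure is not the only outcome.** The rule offers amendment as an alternative, and investigators who saw no toxicity could use it to clarify the definition.

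All four points stand, and they limit the claim to an ambiguity. They do not remove it. The duration was written into one rule and left out of the next, and the same nine patients can score 9/9 or 5/9 depending on the reader. Unresected patients are planned for: all stages are eligible, and the calendar gives them their own dosing and biopsy entries. The inverted trigger does not depend on any of these arguments.

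**Conclusion.** The rule does not work as printed. The inversion is certain from the text: it fires when all patients complete. The missing endpoint is an ambiguity with a mandatory consequence. Read in the evident direction with unresected patients as non-completers, the rule requires amendment or closure without toxicity from 4 unresected of 9 or of 11; with the 6-week milestone it does not.

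The false-trigger probabilities at 9 patients (about 1%, 9%, 27% and 52% at shares of 10%, 20%, 30% and 40%) hold only under the first of those readings and an assumed share. They are not forecasts for this trial. They also apply to one review, whereas the rule is applied repeatedly. The Simon design figures are unaffected. The point should be corrected because the consequence is binding and the repair is small.

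**What to change.** Rewrite the one sentence in Section 12.5 so that the rule fires if fewer than 2/3 of patients enrolled at least 6 weeks before the review have completed 6 weeks of dabrafenib and trametinib, with the modifications allowed in Section 6, whether or not they are resected. This corrects the direction, supplies the endpoint and deals with recently enrolled patients. The sponsor should confirm that the 6-week milestone already used in Section 12.5 is the intended measure. The edit concerns a trial-level monitoring definition and changes no patient's treatment.

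It needs no extra data or patients. There are two small costs. Discontinuations for toxicity after week 6 leave this proportion, though they stay in the cumulative safety and SAE review that Section 12.5 already requires. The safety rule also becomes close to the feasibility rule, adding mainly the look at the end of stage 1.
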